15.3. STATISTICAL ANALYSIS PLAN

All statistical analyses, including interim monitoring, will be conducted using the intent to treat principle, unless explicitly specified otherwise for certain secondary and/or post-hoc analyses. A Bayesian approach will be used for conducting the primary analysis in this trial. We propose to apply a log-binomial regression model and a neutral prior that will be centered at RR=1.0 to final

A Phase II Multi-site Study of Autologous Cord Blood Cells for Hypoxic Ischemic Encephalopathy (HIE) IND 14753 (BABYBAC II)

efficacy and safety data, where final data is defined as data contained in the study database after database lock. Database lock will occur either after 160 infants have completed the study or the study is terminated early for efficacy, futility, or safety. In addition to using a neutral prior, final analyses on locked data and some interim analyses will develop posterior distributions using skeptical (centered at $RR = 1.1$) priors and/or enthusiastic (centered at $RR = 0.625$) priors as well. In all analyses, MCMC methods will be used to sample from the Posterior distribution.

All analyses will involve estimating a Posterior distribution based on a log-binomial regression model with covariates and MCMC methods. In addition to estimating the treatment effect on the log relative risk scale, the log-binomial regression will adjust for level of encephalopathy. For the intercept and the encephalopathy terms, Normal (mean = 0, sd=100) priors will be used. For the term representing the log relative risk, skeptical, neutral, and enthusiastic priors will be used to estimate posterior distributions for the relative risk.

With respect to the primary efficacy endpoint, the estimated Posterior distribution of relative risk based on the data and the neutral prior will be used to determine posterior probabilities of >0 , >10 and $>20\%$ decrease in death or moderate/severe disability, as well as graphical displays of the Posterior distribution and appropriate 95% credible intervals for the relative risk. In addition to adjusting for level of encephalopathy and center in the log-binomial model, the final analysis of efficacy will also perform sensitivity analyses concerning possible treatment effect confounders present at randomization. All additional covariates added to the model will utilize Normal (mean=0, sd=100) priors.

The lack of preexisting data suggests that the neutral prior distribution may be most appropriate for presentation of final results; however, generation of final results using the skeptical (RR of 1.10) and enthusiastic priors (RR of 0.625) will also be produced to give a broad overview of the implications of the trial's efficacy results.

In addition to the analyses specified above, we will also conduct equivalent frequentist analyses using robust Poisson regression to obtain relative risk estimates of the treatment effect adjusted for level of encephalopathy at baseline. Moreover, we will also conduct secondary analyses stratified by inborn or outborn status to estimate the treatment effect separately within each of these two groups.

A Phase II Multi-site Study of Autologous Cord Blood Cells for Hypoxic Ischemic Encephalopathy (HIE) IND 14753 (BABYBAC II)

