6. STUDY DESIGN

This is a prospective, randomized, double-blind, placebo controlled multi-center Phase 2 study in up to 160 infants who meet the NICHD cooling study enrollment criteria and have cord blood collected and available for up to two infusions in the first 48 postnatal hours. We will evaluate the efficacy of the infusions of autologous umbilical cord blood. We project accrual of 60-80 subjects per year. The study will include two groups (up to 80 subjects per group), randomized to receive up to two doses of cells (with a dose range of $2-5 \times 10^7$ cells/kg per dose) or up to two doses of placebo. The randomization will be stratified by severity of encephalopathy, as defined in the NRN's Optimizing Cooling trial¹⁹. Investigators and families will be blinded to enrolled study group.

A Phase II Multi-site Study of Autologous Cord Blood Cells for Hypoxic Ischemic Encephalopathy (HIE) IND 14753 (BABYBAC II)

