8.5.6. FOLLOW UP VISITS

Subjects will return at one year (12 mo - 16 mo) corrected age. The following assessments will be recorded: History and physical exam, Bayley Scales of Infant Development III (BSID), neurological exam, adverse events and concomitant medications. Infants not testable on the BSID due to Cerebral Palsy, blindness or deafness will be assigned scores of 54, 46 and 46 respectively on the cognitive, language and motor of the BSID scale.

A Phase II Multi-site Study of Autologous Cord Blood Cells for Hypoxic Ischemic Encephalopathy (HIE) IND 14753 (BABYBAC II)

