A Phase II Multi-site Study of Autologous Cord Blood Cells for Hypoxic Ischemic Encephalopathy (HIE) IND 14753 (BABYBAC II)

Non-English language learners will be assessed by a bilingual examiner who has been certified or with the assistance of a qualified interpreter. Interpreters must be instructed to translate the Bayley instructions to the child verbatim and to not repeat instructions unless instructed to do so by the examiner. Language scores will not be derived for non-English language learners as the normative developmental progression of language milestones in other languages may not be accurately reflected on the Bayley Language Scales.

11.2.MRI

An MRI is routinely obtained on HIE infants between 7 – 28 postnatal days. Ideally the MRI will be done optimally at 10 days of life (but with an acceptable window between 7 days and 21 days of life as suggested by the 2014 revised guidelines for infants with HIE, to assess extent of injury) ²¹. Results from the standard of care MRI will recorded for the study.

11.3.NICU DISCHARGE

Tracking information will be recorded at discharge, and will include phone numbers and home address. All surviving infants will be followed for one year for the in-person assessment.

An attempt will be made at each site to obtain an autopsy in case of death both prior to and following NICU discharge. Autopsy results, if available, will be included in the case report forms.

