The DSMC may consider proposing termination of the trial for benefit if the upper 95% credible limit for the mean posterior RR of treatment benefit, calculated using a skeptical prior, is less than 1.0. We propose to use a skeptical prior for this consideration to provide a more conservative basis for trial termination, and also to convince even those who strongly believed at the outset that the intervention will not succeed in improving survival free of cognitive impairment. In addition, we note that early stopping of a trial based on treatment benefit generally produces a biased and sometimes misleading estimate of the treatment effect^{28, 29}.

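### Early termination triggers database lock with no provision to wait for the one-year outcomes of infants already randomised, in conflict with the follow-up promised in section 11.3

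*Combined protocol and SAP*

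**What the plan says.** Section 15.3 gives the only rule on database lock: "Database lock will occur either after 160 infants have completed the study or the study is terminated early for efficacy, futility, or safety". The primary model is applied to final data, "where final data is defined as data contained in the study database after database lock". The same section says: "All statistical analyses, including interim monitoring, will be conducted using the intent to treat principle".

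Section 11.3 (NICU Discharge) says: "All surviving infants will be followed for one year for the in-person assessment". It makes no exception for a trial that stops early. Section 8.5.6 sets the timing: "Subjects will return at one year (12 mo - 16 mo) corrected age". Infusions are over by 48 hours of age (section 8.4).

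Early stopping is possible at one formal efficacy and futility look, at a third of primary outcomes and only while recruitment is open (section 13.5). It is also possible at safety looks after every 40 infants (section 13.4). Section 13.6 itself warns that "early stopping of a trial based on treatment benefit generally produces a biased and sometimes misleading estimate of the treatment effect". No section says that lock waits for treated infants to reach their visit, or how an infant without that visit enters the primary analysis.

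**The concern.** Treatment takes two days and the outcome takes a year or more. Whenever the trial stops early, a large group of infants has therefore been randomised and treated but not yet assessed. Their outcomes cost no further exposure, and section 11.3 already commits to collecting them. A lock triggered by termination would leave them out of the final analysis.

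Two things are at stake. The first is precision. The second, after a stop for benefit, is the overestimation that the plan acknowledges. The infants still in follow-up are the data that would pull the estimate back, and an early lock fixes the result at its most extreme point. Section 15.2 says the trial is meant to inform the sample size of a phase III study, so an inflated effect would carry forward.

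A third question is left open. Death counts as failure on the primary outcome, and deaths reach the database quickly because serious adverse events are notified within 24 hours (section 13.2). The locked database may then hold deaths among infants in follow-up without the matching survivors.

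**Working it through.** **The plan's own figures.** The documents give no number of infants without an outcome at an early stop. The nearest figure is the power table in section 15.2 (control event rate 0.60; treated 0.30, 0.35, 0.40, 0.45), which states 0.92, 0.81, 0.62, 0.38. Exact enumeration with a 95% Wald interval on log RR at 60 per arm gives 0.924, 0.803, 0.612, 0.393, so the table is reproduced at 120 infants and the approximation is adequate. The null row comes out at 0.050 against the stated 0.056, which is not matched exactly.

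**Infants without an outcome at the one-third look.** Inputs:
- accrual, section 6: "We project accrual of 60-80 subjects per year";
- lag L of 12 to 16 months (section 8.5.6);
- look at 160/3, about 53 outcomes (section 13.5).

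With uniform accrual at rate r per year, look month = 12 × 53/r + L; enrolled = r × month/12, capped at 160; pending = enrolled − 53 = r × L/12.

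| Rate per year | Lag (months) | Look month | Enrolled | Pending | Share |
|---|---|---|---|---|---|
| 60 | 12 | 22.6 | 113 | 60 | 53% |
| 60 | 16 | 26.6 | 133 | 80 | 60% |
| 80 | 12 | 19.9 | 133 | 80 | 60% |
| 80 | 16 | 23.9 | 160 | 107 | 67% |

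The last row is borderline, because recruitment is all but complete and the look might not be held. More than half are pending when r × L/12 > 53, that is above 53 a year (L = 12) or about 40 a year (L = 16). At an assumed 30 a year the share is 36-43%.

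**Safety looks.** Forty infants are enrolled by month 12 × 40/80 = 6 to 12 × 40/60 = 8, before any 12-month visit, so 100% are pending. After 80 infants 75-100% are pending, and after 120 infants 50-89%.

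**Precision.** Take 0.60 against 0.375, that is RR 0.625, the centre of the enthusiastic prior. SE(log RR) = √[(0.4/0.6 + 0.625/0.375)/n] = √(2.333/n) with n per arm.
- n = 26.5: 0.297.
- n = 56.5: 0.203.
- n = 80: 0.171.

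Power against a treated rate of 0.35 (two-proportion test) is 0.44 with 53 infants, 0.76 with 113 and 0.83 with 133.

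**Estimate after a benefit crossing.** This was simulated with 27 per arm and a normal approximation to the posterior. A crossing is an upper 95% limit below 1. Crossing trials were then continued to 56-80 per arm.

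| True RR | Crossing, vague prior | Median RR at the look | Median RR, all followed |
|---|---|---|---|
| 0.625 | about 35% | 0.47 | 0.54-0.56 |
| 0.75 | about 17% | 0.50 | 0.62-0.66 |

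At RR 0.625, follow-up recovers (0.54 − 0.47)/(0.625 − 0.47) = 45% to (0.56 − 0.47)/0.155 = 58% of the overstatement.

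Section 13.6 bases the benefit rule on a skeptical prior centred at 1.1 but gives no spread. With an assumed SD of 0.35 to 1.0 on log RR, a crossing occurs in about 4% to 27% of trials at RR 0.625. At SD 1.0 the median RR, estimated without the prior, is 0.44 at the look against 0.53-0.56.

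**Deaths among pending infants.** Suppose their deaths are counted and their survivors dropped. With P pending and death rate d, the expected event rate in an arm is (53p + Pd)/(53 + Pd).
- Deaths 24% in both arms (low end of the range in section 5), true RR 0.60 (0.36 against 0.60), P = 60: (31.8 + 14.4)/67.4 = 0.685 for control and (19.08 + 14.4)/67.4 = 0.497 for treated, RR 0.73. With P = 107, RR 0.78. The estimate moves towards 1.
- Deaths 11% against 0% (the phase I in-hospital figures, section 5.2), no true effect on the composite: RR 0.93 (P = 60) to 0.89 (P = 107). The estimate moves away from 1.

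**The case against.** The strongest reply is that the plan never says follow-up ends, or that pending infants are excluded. The word for timing in the lock sentence can govern both branches, so termination may be only a precondition for lock, and section 11.3 then supplies the missing step. This stands as far as it goes: a reader might infer that the documents plainly order exclusion, and they do not. They conflict. But section 11.3 governs visits, while section 15.3 alone governs lock and the analysis set, and it contains no waiting step. Even on the benign reading the sentence needs correcting.

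Other stronger readings also fail.
- A reader might infer that most infants would be missing at any early stop. That depends on accrual, and section 13.5 justifies the look by possibly slow enrolment. With the 120 infants named in section 13.7 as the target, the look falls before recruitment closes only at 60 a year with a 12-month lag (60 of 100 pending).
- A reader might infer that over-represented deaths bias the result in a known direction. The plan does not say whether those deaths enter the model, and the two cases above go opposite ways. If pending infants are simply left out, deaths are not over-represented.
- A reader might infer that the lock rule contradicts intent to treat. That principle sets no lock date. What is missing is a rule for incomplete outcomes.
- A reader might infer that the 160-infant trigger can never be met if one infant is lost. That turns on what it means to complete the study, which is undefined.

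A benefit stop is also not the likely course. Crossing is a minority event in every case examined, and the committee has discretion. The overestimate is conditional on that event.

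**Conclusion.** The point holds as a conflict between sections 15.3 and 11.3, whose literal resolution gives a worse final analysis. At the projected accrual and a target of 160, a stop at the one-third look would lock with 53-67% of randomised infants lacking a one-year outcome, and with a standard error about 1.5 to 1.7 times as large as with all of them followed (0.297/0.203 to 0.297/0.171). After a benefit crossing, roughly half of the overstatement of effect would be left in place when it could have been removed. A first-look safety stop would leave the primary outcome with no Bayley data.

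These sizes rest on uniform accrual at 60-80 a year, event rates of 0.60 and 0.375, and a normal approximation. The crossing frequencies also depend on prior spreads that the plan does not state. The direction of any bias from deaths among pending infants is uncertain. The conflict in the text depends on none of these assumptions.

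**What to change.** Replace the lock sentence in section 15.3 with: *If enrolment stops early for any reason, all randomised infants are followed to death or the 12-16-month visit. In all cases the database is locked once every randomised infant has died, completed that visit, or passed the end of the visit window. The final analysis includes all randomised infants.*

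Label the result at the stopping look as interim. State how infants without a one-year assessment enter the primary model, including deaths recorded before the visit was due. Make the change before any interim look.

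The new wording also removes the dependence on 160 completers when enrolment is only up to 160. The cost is a short text amendment and, after an early stop, a final report up to about 16 months later. The visits are those section 11.3 already promises, and the monitoring committee's decisions are not affected.

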The improved survival and one-year neurologic outcomes of subjects who received cells and concurrent cooling compared to cooled infants who did not receive cells provide impetus to move forward to a multi-center phase II placebo controlled study. Since publication of the phase I paper in May 2014, we have accumulated and reported additional data on infants with HIE and one year outcomes²⁵. Thirty-nine (39) infants have been cooled and received cells (16 since our initial report) and 146 have been cooled for HIE without receiving cells. For those receiving cells, median collection and infusion volumes were 33 mL and 5 mL. None of the cell recipients died prior to discharge while 16 (11%) of cooled non-cell recipients died prior to hospital discharge ($p = 0.03$). Ten (26%) cell recipients and 31 (21%) cooled-only infants were discharged on seizure medications ($p = 0.56$). Of the 25 cell recipients with known one year

A Phase II Multi-site Study of Autologous Cord Blood Cells for Hypoxic Ischemic Encephalopathy (HIE) IND 14753 (BABYBAC II)

outcomes, 16 (64%) survived with Bayley III scores ≥ 85 in all three domains, and of the 63 cooled-only infants with known one year outcomes, 25 (40%) survived with one year Bayley III scores ≥ 85 in all three domains ($p = 0.04$). While the results for the cell recipients are better than for infants who were cooled, important facts must be acknowledged. More of the cell recipients were inborn, and more of the cooled only group were not seen at one year follow-up.

[figure not shown]

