11.4. SHORT TERM/HOSPITAL OUTCOMES/STUDY ENDPOINT

Short term outcomes will be considered secondary outcomes for the study. We will compare adverse outcomes, including mortality, seizures, need for nitric oxide and need for ECMO, need for G-tube feeding at discharge, and discharge on anti-epileptic medications. This information will be collected in case report forms.

11.5.LONG TERM OUTCOMES/PRIMARY OUTCOME/STUDY ENDPOINT

The Primary outcome of the study will be survival at one year with Bayley III scores in all three domains ≥ 85 .

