12. RISKS AND BENEFITS

12.1.RISK AND BENEFITS OF STUDY

Infusion of a neonate's own cord blood cells during routine cooling is hoped to improve survival and neurological outcome as compared to infants that are only cooled and receive red blood cells. Autologous cells should eliminate any risk of graft vs host reaction. If cord blood cells are collected and not infused, cord blood cells will be cryopreserved for later autologous use for the subject. Complications of cord blood infusions could include infection, volume overload, hypertension, allergic or anaphylactic reactions, hyperviscosity or pulmonary edema and will be

A Phase II Multi-site Study of Autologous Cord Blood Cells for Hypoxic Ischemic Encephalopathy (HIE) IND 14753 (BABYBAC II)

monitored during and after infusion. The medication hydrocortisone given prior to the infusions may increase blood sugar, blood pressure and fluid retention.

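### Final safety data are analysed only as relative risks with an unstated prior SD, so for a rare harm with no events in one arm the size of the reported effect depends heavily on that SD

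*Combined protocol and SAP*

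**What the plan says.** Section 15.3 sets the final model: "We propose to apply a log-binomial regression model and a neutral prior that will be centered at RR=1.0 to final" "efficacy and safety data, where final data is defined as data contained in the study database after database lock". It then generalises: "All analyses will involve estimating a Posterior distribution based on a log-binomial regression model with covariates and MCMC methods". On priors it says "For the intercept and the encephalopathy terms, Normal (mean = 0, sd=100) priors will be used", and for the treatment effect "For the term representing the log relative risk, skeptical, neutral, and enthusiastic priors will be used to estimate posterior distributions for the relative risk". Those three treatment priors are centred at RR 1.1, 1.0 and 0.625. No SD is given for any of them, in 15.3 or elsewhere.

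Section 15.3 also adds a frequentist robust Poisson analysis, again giving a relative risk. No risk difference, exact interval or rule for an empty arm appears.

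The outcomes at issue are the individual adverse events listed in sections 13 and 13.4 (allergic reaction, hemoglobinuria and polycythemia among them) and the hospital outcomes of section 11.4: "We will compare adverse outcomes, including mortality, seizures, need for nitric oxide and need for ECMO". Section 12.1 names further possible complications, including "allergic or anaphylactic reactions, hyperviscosity or pulmonary edema". Section 5.2 shows that an empty arm has already occurred in this programme: "None of the cell recipients died prior to discharge while 16 (11%) of cooled non-cell recipients died prior to hospital discharge".

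**The concern.** If one arm has no events, the data put a limit on the RR on one side only. The likelihood keeps rising, or stays flat, as the log RR runs off towards minus or plus infinity. What keeps the posterior finite is the prior on the log RR, and the plan does not give its width. Two analysts who both follow section 15.3 could therefore report very different effects from the same counts, one with an interval that includes 1 and one with an interval that excludes it. Running the skeptical, neutral and enthusiastic priors does not expose this, because they are distinguished only by their centres.

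Safety is part of the primary objective in section 4, and this phase II trial is meant to inform a phase III design. Rare harms are where a reader most needs a summary that reflects the counts.

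**Working it through.** **Inputs.** Up to 80 infants per arm (section 6). Neutral prior centred at RR 1.0 and intercept prior Normal(0, SD 100) (section 15.3). Phase I deaths before discharge 0/39 v 16/146 (section 5.2). The treatment-prior SD is not in the documents, so a range is used. The severity term is omitted.

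**The plan's own figure.** For 0/39 v 16/146, chi-square without correction gives p = 0.0305 and Fisher's exact test p = 0.026. Both round to the stated 0.03.

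**Model.** Write p0 and p1 = p0 × RR (less than 1) for the placebo and cell risks, and x0 and x1 for the events. The posterior is proportional to

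p1^x1 (1 − p1)^(80 − x1) × p0^x0 (1 − p0)^(80 − x0) × N(log p0; 0, 100) × N(log RR; 0, SD).

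If x1 = 0, the only likelihood term containing RR is (1 − p0 × RR)^80. It rises to 1 as RR goes to 0, so there is no finite maximum in log RR. The same holds in the other direction if x0 = 0.

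**Posterior median RR (95% credible interval), by numerical integration, cells v placebo.** The count of 9/80 applies the Phase I 11% to 80 infants (8.8, rounded). The other counts are illustrative.

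| Events per 80 | SD 0.35 | SD 1 | SD 2 |
|---|---|---|---|
| 0 v 9 | 0.63 (0.35–1.16) | 0.20 (0.05–0.65) | 0.06 (0.004–0.38) |
| 2 v 0 | 1.12 (0.58–2.19) | 2.0 (0.40–10.9) | 5.3 (0.44–115) |
| 3 v 1 | 1.12 (0.59–2.14) | 1.70 (0.42–7.4) | 2.54 (0.40–23) |
| 4 v 9 | 0.79 (0.44–1.41) | 0.53 (0.19–1.37) | 0.46 (0.14–1.31) |
| 48 v 40 | 1.17 (0.90–1.53) | 1.20 (0.90–1.60) | 1.20 (0.90–1.61) |

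For 0 v 9 the median moves about tenfold (0.63/0.06) and the interval goes from including 1 to excluding it. With events in both arms the estimate settles as the prior widens: near 0.43 for 4 v 9, and at 3.5 to 3.9 for 3 v 1 from SD 5 upwards. For a common composite the SD hardly matters.

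**Robust Poisson.** Fitted to 0/80 v 9/80, it returns a log RR of −22.4 with a standard error of 0.33. This is a non-converged value with false precision.

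**How often an arm is empty.** P(no events in an arm of 80) = (1 − p)^80. P(at least one empty arm) = 1 − [1 − (1 − p)^80]². The event risks p are assumptions, the same in both arms.

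- p = 1%: 0.99^80 = 0.4475, giving 1 − 0.5525² = 0.69.
- p = 2%: 0.98^80 = 0.1986, giving 1 − 0.8014² = 0.36.
- p = 5%: 0.95^80 = 0.0165, giving 0.033.
- p = 11%: (1 − p)^80 is about 0.0001, giving about 0.0002.

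**Risk difference on the same counts (Newcombe 95% interval).** This needs no prior on the log RR.

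- 0/80 v 9/80: −11.3 points (−20.0 to −4.3).
- 2/80 v 0/80: +2.5 points (−2.4 to +8.7).
- For an arm with 0/80, the one-sided exact 95% upper bound on risk is 1 − 0.05^(1/80) = 3.7%.

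**The case against.** **Scope.** A reader might infer that every safety outcome is reported only through the log-binomial model. The documents do not support that. Section 15.3 adds robust Poisson. Section 13.4 rests the interim safety comparison on a composite of all listed events and gives the monitoring committee the full posterior, two sets of priors and an exploratory class of priors. Section 13.6 uses logistic regression for interim efficacy, so the universal sentence in 15.3 is loosely worded. Section 11.4 names no model, and no section explicitly commits to a separate regression for each adverse event. All of this narrows the point. It does not remove it, because robust Poisson fails on the same tables and the interim provisions supply no final analysis for a single rare event.

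**Prior against data.** It is tempting to say that the prior sets the result and the data do not. That goes too far. For 0 v 9, P(RR > 1) is 0.18 or less at every SD tried from 0.2 upwards, so the direction comes from the data. The size and the interval are what depend on the SD.

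**Deaths.** A reader might expect the Phase I pattern of no deaths to recur. That is improbable: the chance of no deaths in 80 is 0.0001 at 11% mortality and 0.017 at 5%, and section 5 cites 24 to 38% in cooled infants. Phase I was non-randomised and counted only deaths before discharge. The 0 v 9 table illustrates the mechanism and is not a forecast.

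**Extreme SDs.** An SD of 100 would give absurd results, but section 15.3 gives that value only for other terms. At SD 1 to 2 the model behaves reasonably. The SD cannot be recovered from the table in section 15.2: at 60 per arm four of the interval widths suit an SD near 1, while the fifth row suits 0.35 better.

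**The alternative has priors too.** For 2 v 0, the beta-binomial probability of higher risk with cells is about 0.93 with Jeffreys priors and 0.88 with uniform priors. This stands, and it is why one method must be named in advance.

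**Conclusion.** The point holds for individual rare safety outcomes in the final analysis when one arm has no events. There the RR, its interval and the exclusion of 1 depend heavily on an SD that the plan does not state. Over assumed SDs of 0.35 to 2 the median runs from 0.63 to 0.06 for 0 v 9, and from 1.1 to 5.3 for 2 v 0. The companion model has no finite estimate.

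It does not hold for the common composite, nor for outcomes with adequate events in both arms unless the prior is tight. It does not touch the primary endpoint.

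The conclusion rests on 80 per arm, no severity adjustment, the assumed SD range, and reading 15.3's reference to safety data as covering individual events. How often it would matter rests on assumed event risks of 1 to 2%. It is a statistical matter only and raises no question of clinical management. The change should be made, and it is small.

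**What to change.** In section 15.3:

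1. State the SD of each treatment prior (skeptical, neutral, enthusiastic) on the log-RR scale.
2. For every individual adverse event and every section 11.4 hospital outcome, report event counts and risk by arm, and the risk difference with a 95% interval, alongside the RR. Name one interval method in advance, for example Jeffreys beta-binomial or Newcombe.
3. Where either arm has no events, base the conclusion on the risk difference and do not report the log-binomial or robust Poisson RR.
4. Keep the severity-adjusted log-binomial RR for the primary endpoint, the composite and outcomes with events in both arms.

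Limiting the switch to empty arms keeps the planned adjustment wherever the RR can be estimated, which a rule such as fewer than five events would not do (4 v 9, for instance).

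The cost is a short SAP paragraph and a few lines of code, with no new data and no change to sample size or the primary analysis. The one small loss is that zero-cell comparisons are not severity-adjusted.
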